Although no observational study can claim to be free from confounding, the preliminary results from KPSC demonstrate that we can identify and account for the differences between groups in the methods that we are using. It is worth noting that at this point a randomized trial (the only sure way to avoid confounding) would be unethical. Further, this is a study of the safety of these agents so we anticipate finding either that there are safety problems or that there are not safety problems and either result, with an adequately powered study, will be useful to patients and their physicians who are making decisions about this treatment.

Missing data

At the KP sites the EHR is relatively mature. Based on our experience in the pilot study, we do not anticipate much missing data for typical data elements like treatments, demographics, vital signs, and lab values. We will run usual checks on variables to identify the rate of missing data for key variables and will identify variables with more than 5% of missing data. The OneFlorida sites carefully monitor the fields that are submitted with valid data. OneFlorida partners were asked to submit enhanced laboratory data with elements that are not included in the PCORnet Common Data Model. These enhanced laboratory data are necessary for the HCV study and others. UFHealth, Health Choice Network, Florida Hospital, and Tallahassee Memorial Hospital, which comprise the major providers within OneFlorida. We do not anticipate much missing data.

For most EHR based data elements we anticipate very low levels of missing data, typically less than 1%. For example, missing rates in the KPSC Hep C populations are: eGFR – 1.0%, Gender – 0.1%, Age – 0.1%, Race – 4.0%. Race imputation will be performed using the BISG algorithm from RAND. These values are already routinely calculated in the KP system. Other values will be imputed with mean value substitution. Sensitivity analysis will be performed by comparing to complete case analysis. Should

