there be evidence that this missing data is influential full multiple imputation will be employed. Perhaps not best thought of as missing data there are variables that may be drivers of the treatment decision that may not have been collected. Potentially the most important of these is the MELD score of liver function with a missing rate of nearly 10%. The decision to collect the elements of the MELD score is likely a function of health status. It may be necessary to treat the decision to generate a MELD score as an endogenous process and use structural equation models to understand the effects of MELD scores on the treatment decision.

If more than trivial amounts of missing data occur, we will use multiple imputation and the corresponding analysis procedures to incorporate the estimated effects of imputation on coefficients and their standard errors. Disenrollment can be handled directly in the MSM model with an incorporated model for censoring.

Dropout will result primarily from a lapse in membership or death. Membership and death records are kept by the insurer and will be used to record and report dropout. As this is a retrospective analysis of data collected during patient care and stored in the EHR, reasons for missing labs and demographics will be unknown and not reported.

A complete case analysis will be compared to imputation based analysis.

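### Mean substitution is the default for missing covariates, the switch to multiple imputation has no threshold, and no method is fixed for MELD

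*SAP*

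**What the plan says.** All of this is in the SAP's Missing data section unless noted.

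- **Expected level.** "For most EHR based data elements we anticipate very low levels of missing data, typically less than 1"%. The examples follow: "missing rates in the KPSC Hep C populations are" eGFR 1.0%, gender 0.1%, age 0.1% and race 4.0%. No rates are given for the other sites.
- **Flag.** After routine checks the team "will identify variables with more than 5% of missing data". Nothing is said to follow from the flag.
- **Default.** Race is imputed by BISG. For the rest: "Other values will be imputed with mean value substitution".
- **First route to multiple imputation.** "Sensitivity analysis will be performed by comparing to complete case analysis". The next sentence says that should "there be evidence that this missing data is influential full multiple imputation will be employed".
- **Second route.** After the MELD discussion, the plan commits to multiple imputation, with matching standard errors, if the amount of missing data is more than trivial. No percentage is given.
- **MELD.** It is introduced as potentially the most important of the treatment drivers that may not have been collected: "the MELD score of liver function with a missing rate of nearly 10"%. Such variables are "Perhaps not best thought of as missing data". Collection is said to depend probably on health status, and a structural equation model is mentioned as something that may be needed.

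Under Marginal Structural Modeling, the treatment model conditions on all observed covariates. Under Overview, each outcome is modeled separately.

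**The concern.** Single mean substitution gives every patient with a missing value the same value. Among those patients the covariate no longer separates sicker from healthier, so adjustment for it fails there. This matters little at 0.1% or 1% missing. It can matter for a strong treatment driver that is nearly 10% missing, and MELD is the only variable with a quoted rate above the plan's own 5% flag.

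Three things are left open:

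- what would count as influential, and on which estimates it would be judged;
- what amount is more than trivial, and whether the 5% flag was meant to define it;
- which method applies to MELD.

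If influence is judged from fitted estimates, the imputation method can depend on the result. It could also differ between outcomes, or between the Poisson and MSM analyses.

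What is at stake is residual confounding in a safety comparison. If sicker patients are treated less, it makes DAA look safer than it is; if they are treated more, the same reasoning gives the opposite sign.

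**Working it through.** The SAP gives no sample size, event count or effect size on this point, so there is no plan figure to reproduce.

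**1. How many patients are affected.** Inputs are the SAP's rates of 1.0%, 0.1%, 0.1% and 4.0%, with MELD taken as 10%. The share with at least one missing value lies between the largest rate and the sum of the rates.

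- With MELD: 10.0% to 1.0 + 0.1 + 0.1 + 4.0 + 10.0 = 15.2%. Under independence, 1 − 0.99 × 0.999 × 0.999 × 0.96 × 0.90 = 14.6%.
- Without MELD: 4.0% to 5.2% (5.1% under independence).

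Most of the missingness therefore comes from the variable whose method is open.

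**2. A simple Poisson check (all parameters assumed).** One standard-normal confounder has coefficient 0.7 on the log rate and −0.7 on the treatment logit. The true IRR is 1, 10% of values are missing, and n = 2,000,000. The share of confounding left is ln(IRR mean-substituted / IRR full) ÷ ln(IRR unadjusted / IRR full).

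| Missingness | Unadjusted | Full data | Mean-substituted | Complete case | Share left |
|---|---|---|---|---|---|
| Random | 0.642 | 1.004 | 0.953 | 1.002 | 0.052/0.447 = 12% |
| More at low values (slope 1) | 0.638 | 0.994 | 0.947 | 0.993 | 0.048/0.442 = 11% |
| More at low values (slope 2) | 0.642 | 1.002 | 0.937 | 1.002 | 0.067/0.445 = 15% |

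**3. A simulation closer to the plan (all parameters assumed).**

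- Size: 20,000 patients, 6 periods, 25 replicates, about 1,900-2,400 events, 30-34% treated.
- Effects: no true treatment effect; sicker patients treated less.
- MELD: time-varying, correlated 0.5 with a health-status covariate, missing for whole patients. Its effect on both treatment and outcome is 0.25 (weak), 0.5 (moderate) or 0.8 (strong) logit per SD.
- Mechanisms: completely random, related to health status, mostly low MELD, mostly high MELD.
- Models: stabilized-weight MSM, and Poisson with covariates frozen at initiation.

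The table gives the percentage shift of the estimate against full data, as the range over mechanisms.

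| Method | Weak | Moderate | Strong |
|---|---|---|---|
| Mean substitution, 10% missing, MSM and Poisson | −0.5 to −1.0 | −2.6 to −4.5 | −6.3 to −11.8 |
| Same, health status also adjusted for, MSM only | −0.6 to −1.0 | −1.9 to −3.8 | −4.7 to −9.9 |
| Mean substitution, 5% missing | −0.3 to −0.5 | −1.3 to −2.5 | −3.0 to −6.4 |
| Mean substitution, 1% missing, largest | −0.2 | −0.6 | −1.5 |
| Multiple imputation, 10% missing | +0.3 to −0.4 | −0.1 to −1.1 | +0.1 to −2.8 |

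Monte Carlo standard errors at 10% missing are at most 0.11, 0.29 and 0.61 percentage points. For the health-status-adjusted row (12 replicates) they reach 0.65.

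Omitting MELD altogether shifts the MSM estimate by −5.6%, −21.0% and −42.9%, and the Poisson estimate by −6.0%, −22.1% and −44.7%. On the log scale, mean substitution at 10% missing leaves 8% to 22% of that. For example, in the strong MSM case, ln(1 − 0.118)/ln(1 − 0.429) = 0.126/0.560 = 22%. The simple check's 11-15% falls inside this range.

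**4. Scale against precision.** With about 2,000 events, the moderate shift of 2.6-4.5% is about 0.4 to 0.7 of a standard error. The pooled multiple-imputation standard error exceeds the mean-substitution one by only 0.1-0.5% (weak), 0.3-1.9% (moderate) and 0.8-5.7% (strong). Bias is the main issue, not understated variance.

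**The case against.** A reader might infer that the two conditions contradict each other. They do not: each is sufficient and both lead to multiple imputation. A variable with much missing data that is not judged influential still qualifies under the second. The fault is only that neither is quantified.

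A reader might also infer that the plan will mean-substitute MELD. The text does not support that. The commitment to multiple imputation comes directly after the MELD discussion, and nearly 10% is hard to call trivial beside a usual level below 1%. The remark that such variables are "Perhaps not best thought of as missing data" cuts both ways: if it takes MELD outside the multiple-imputation rule, it equally takes it outside the mean-substitution rule. What stands is that MELD's method has to be inferred. The structural equation model does not settle it, since its stated aim is to understand the treatment decision, not to supply a value for the models.

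That the choice would be driven by results is also an inference, from the position of the influence sentence right after the complete-case comparison. The switch is stated only towards multiple imputation. The complete-case comparison is a real safeguard: in the simple check complete cases gave about 1.00 where mean substitution gave about 0.95. But the plan says nothing about how large a difference would count.

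Finally, the bias figures depend on assumed effects, and the covariate list may be in the protocol, so it is not certain that MELD enters the models. Adjusting for health status lowers the largest MSM shift from 4.5% to 3.8% (moderate) and from 11.8% to 9.9% (strong). These points limit the size claimed but do not supply the missing rule.

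**Conclusion.** The concern holds as a weakness in a stated method. Mean substitution is the written default, the route away from it has no threshold, the 5% flag has no consequence, and the method for MELD is probably multiple imputation but is not fixed.

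The bias is conditional on MELD entering the treatment or outcome models and being mean-substituted. At 10% missing it is then about 1% or less under weak, about 2-5% under moderate and about 5-12% under strong assumed confounding. At 1% missing, about the level the SAP expects for most variables, it is negligible to small. These figures illustrate a range and do not predict this study's bias. The downward direction rests on the assumption that sicker patients are treated less; the opposite case was not simulated.

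This is worth correcting before outcome models are fitted. It does not by itself invalidate the planned analyses.

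**What to change.** Replace mean substitution with multiple imputation as the primary method from the outset, for MELD and every other incomplete covariate except race, which stays with BISG.

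- Include treatment, outcome, time and predictors of health status in the imputation model. Because outcomes are modeled separately, include all of them or impute per outcome.
- Re-estimate the weights within each imputed dataset, then pool.
- Drop the two conditions for switching, which become unnecessary. Use the 5% flag for reporting, overall and by site.
- Keep the complete-case analysis as a sensitivity analysis.
- Optionally, add a sensitivity analysis that shifts the imputed MELD values over a range fixed in advance.

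Tying multiple imputation to the 5% flag alone would be weaker. A variable just below the flag would stay on mean substitution, and at 5% missing the simulated shift still reached 2.5% (moderate) and 6.4% (strong).

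The cost is SAP wording and modest computing, since multiple imputation is already the plan's fallback. Some bias can remain if missingness depends on the unobserved MELD value: in the simulation up to about 1.1% under moderate and 2.8% under strong confounding. The shifted-imputation analysis would address this.
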